as Random Regression Modeling and Hierarchical Linear Modeling) which takes advantage of all existing data points for minimal loss of data, will be used to analyze the data related to our main hypothesis (H1a). Therefore, we will not impute missing data because our analytic method uses all existing data points, including all subjects with missing data or those who were terminated early in the study, without relying on data imputation procedures (Diggle et al., 1994; Laird & Ware, 1982; Hedeker et al., 1991). The mixed effects approach provides more information and, therefore, more power compared to cross-sectional analyses that focus on the analysis of one summary index or more traditional analytic approaches such as a change score, end-point, or repeated measures analysis of variance (ANOVA). We will also use pattern-mixture models to assess if there is bias due to drop out or missing data. As described by Hedeker and Gibbons (1997), these mixed models allow us to assess whether important estimates are dependent on missing data patterns, and provide overall estimates of effects by averaging over the various missing-data patterns. In addition, we will consider the extension of the Pattern-Mixture models as described by Guo et al. (2004), which includes the incorporation of random effects in the pattern mixture model, allowing subject-to-subject heterogeneity. Missing data will be examined to assess randomness. The pattern of missing data will be examined according to the procedure recommended by Little and Rubin (1987), which includes comparing group differences in the primary outcomes of subjects with versus without missing data. SPSS and SAS statistical software will be used to analyze the data. Type I error will be controlled by a Bonferroni adjustment to the alpha per outcome domain for Hypotheses 1a and 1b. Specific plans for testing each hypothesis are below.

H1a: Positive CCT-associated effects on cognition, functional capacity (co-primary outcomes), and disability will emerge over the 15-week study.

Dependent variables: Cognition (global deficit score [GDS] composite; Heaton, et al., 1995), UPSA-B (co-primary outcomes), WHODAS 2.0.

Independent variables: Treatment group (CCT vs education control) and Time (0, 5, 10, 15 weeks).

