Statistical analyses: We will analyze data on all randomized subjects with a baseline assessment and at least one post-baseline evaluation, using mixed effects models, described above. The mixed effects model method provides an estimate of the individual variability around the population trend, the variability of the individual intercepts (baseline values) and slopes (changes across time), and the correlation between them. A fully saturated treatment by time model will be utilized for inference. Covariance structure will be chosen based on Akaike's Information Criterion (AIC). Random group level treatment effects will also be evaluated for importance based on the model AIC. This method allows for any group level effects to be incorporated into the model. Denominator degrees of freedom will be calculated using the Kenward-Roger small sample correction.

Power Analysis: We used procedures described by Hedeker et al. (1999) for Random Regression Models for the proposed study to estimate needed sample size (the RMASS program provided by Hedeker). We estimated that with a final sample size of 78 (target n=98, with a drop-out rate of 20%), the study will have .80 power to yield a statistically significant result for a .72 effect size, accounting for Type I error correction, .5 correlation between time points, and one random effect in the model. We have previously found CCT-associated effect sizes of .72 for prospective memory functioning in Veterans with mild to moderate TBI (74% of whom had PTSD), as well as for the UPSA-B in individuals with severe mental illness. Although we have not previously used the WHODAS 2.0 to assess disability, we have also found CCT-associated effect sizes of .81-1.0 for quality of life in these populations. The trial was therefore powered to detect effect sizes in the .72 range.

H1b: Positive CCT-associated effects on community reintegration outcomes (housing stability, participation in employment/education, healthcare appointment attendance) will be detected at the end of the 1-year follow-up.

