Dependent variables: Proportion of months housed, proportion of months engaged in productive activity (work or school), and proportion of VA healthcare appointments attended during the 1-year follow up period (all three outcomes based on monthly data collected during the 1-year follow-up period). Any missing data on housing and work/school status will be accounted for by using a proportion based on the available data points. Healthcare appointment attendance will be gathered from CPRS data and will not be subject to missing data.

Independent variable: Treatment group (CCT vs education control).

Statistical analyses: ANOVA models comparing the treatment and control group on the three dependent variables above. We have selected ANOVA over alternative models (t-test; Wilcoxon Rank Sum; Poisson regression) due to the type of dependent variables (continuous) and the option to include any covariates that might be imbalanced between the treatment groups.

Power analysis: With 78 subjects (39 subjects per group), we will have .80 power to detect an effect size of .64, a medium-to-large effect size.

capacity, disability, and community reintegration.

Dependent variables: UPSA-B at 15 weeks, WHODAS 2.0 at 15 weeks, proportion of months housed, proportion of months engaged in productive activity (work or school), and proportion of VA healthcare appointments attended during the 1-year follow up period.

Independent variables: Treatment group (CCT vs education control).

Mediators: Cognitive improvement in GDS composite from 0-10 weeks (slope of change across weeks), improvement in CPSA cognitive strategy use from 0-10 weeks (slope of change across weeks).

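### H1a names no primary test within its saturated treatment-by-time model and leaves baseline unconstrained, so the stated .80 power belongs to no defined test and is not assured for the natural 3-df interaction test

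*Combined protocol and SAP*

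**What the plan says.** All references are to the Combined protocol and SAP, Section 9, Analytic Plan and Power Analyses.

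- **Hypothesis.** H1a expects positive effects on cognition, functional capacity and disability that "will emerge over the 15-week study". No visit is singled out.
- **Outcomes.** The global deficit score is listed with "UPSA-B (co-primary outcomes), WHODAS 2.0": two co-primaries and a third outcome.
- **Independent variables.** "Treatment group (CCT vs education control) and Time (0, 5, 10, 15 weeks"). Week 0 is thus a level of the time factor, and the text describes the random intercepts as the baseline values.
- **Test.** "A fully saturated treatment by time model will be utilized for inference". No interaction test, visit or contrast is named, and nothing constrains the two arms to a common baseline mean.
- **Multiplicity.** "Type I error will be controlled by a Bonferroni adjustment to the alpha per outcome domain for Hypotheses 1a and 1b". No numerical alpha is given and visits are not mentioned.
- **Power.** With 78 analysed, "the study will have .80 power to yield a statistically significant result for a .72 effect size", after Type I error correction, with correlation .5 between time points and one random effect. Nothing says at which visit, or for which contrast, the .72 applies.
- **Elsewhere.** H2 takes "UPSA-B at 15 weeks, WHODAS 2.0 at 15 weeks" as dependent variables. That is a choice for the mediation analysis and not a statement about H1a.

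**The concern.** With two arms and four visits, a saturated model has three treatment-by-time parameters. They can be tested jointly on 3 df, one visit at a time, or through a weighted combination. These tests differ in power, and the ranking depends on how the effect develops. The power statement gives one effect size and no profile over visits, which is what a 1-df test needs and less than a 3-df test needs.

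This is the plan's main hypothesis. If the test stays open, the .80 cannot be attached to the analysis that will be run, and the choice of test or visit could be made after the data are seen. In addition, treating week 0 as a free outcome time makes every comparison a change from baseline. At a correlation of .5 that discards precision which the collected data already offer.

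**Working it through.** **Inputs.** From Section 9: 39 per arm (78 in total), effect .72 SD, r = .5, visits at 0, 5, 10 and 15 weeks. Assumed, because the plan does not say: two-sided alpha of .05/2 = .025 (two co-primaries), with .05/3 = .0167 (three outcomes) as the alternative; compound symmetry (the reading of one random effect); 39 complete cases per arm, ignoring partial data from dropouts.

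**1. The plan's own figure.** For one contrast with SD 1, the noncentrality is .72/√(2/39) = .72/.2265 = 3.18. A change from baseline has variance 2(1 − r) = 1 at r = .5, so it gives the same value. With 76 df, power is .81 at alpha .025 and .77 at .0167 (normal approximation .83 and .78). The stated .80 fits a single 1-df contrast. A difference averaged over all four visits (.96) or a linear slope (.87), both at .025, does not give .80.

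**2. The 3-df test.** The noncentrality is λ = (39/2) δ′V⁻¹δ, where δ holds the effects at weeks 5, 10 and 15.

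- Baseline unconstrained: V is the covariance of the three changes, with variance 2(1 − r) = 1 and covariance 1 − r = .5. Then δ′V⁻¹δ = [Σδ² − .25(Σδ)²]/.5.
- Baseline means equal: V is the covariance given baseline, with variance 1 − r² = .75 and covariance r − r² = .25. Then δ′V⁻¹δ = [Σδ² − .20(Σδ)²]/.5.

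For linear growth (.24, .48, .72), Σδ² = .8064 and (Σδ)² = 2.0736.

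- Unconstrained: λ = 19.5 × (.8064 − .5184)/.5 = 11.23.
- Constrained: λ = 19.5 × (.8064 − .4147)/.5 = 15.28.

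Power comes from the noncentral F with 3 numerator df. Each range runs from 74 denominator df (unstructured covariance) to 228 (compound symmetry).

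| Effect at weeks 5 / 10 / 15 | λ, unconstrained → constrained | 3-df unconstrained, .025 | same, .0167 | 3-df constrained, .025 | same, .0167 |
|---|---|---|---|---|---|
| .24 / .48 / .72 (linear) | 11.23 → 15.28 | .70–.72 | .64–.67 | .85–.87 | .81–.83 |
| .36 / .72 / .72 (full by week 10) | 13.90 → 20.22 | .81–.83 | .76–.78 | .94–.95 | .92–.94 |
| .72 / .72 / .72 (full by week 5) | 15.16 → 24.26 | .85–.86 | .80–.83 | .98 | .97 |

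**3. Dependence on r.** The unconstrained λ scales with 1/(1 − r). For linear growth at alpha .025, unconstrained power is .52–.54 at r = .3, .81–.83 at r = .6 and .92–.93 at r = .7.

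**4. A single week-15 contrast.** Baseline adjustment changes the variance from 2(1 − r) = 1 to 1 − r² = .75, so the noncentrality rises from 3.18 to .72/√(.75 × 2/39) = 3.67. Power rises from .81 to .91 at .025, and from .77 to .89 at .0167. The variance ratio is (1 + r)/2, which is below 1 for any r < 1, so the gain is not special to week 15.

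**5. Week 15 against the joint test, both baseline-adjusted, alpha .025.**

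- Linear: .91 against .85–.87.
- Full by week 10: .91 against .94–.95.
- Full by week 5: .91 against .98.
- Effect halved after treatment ends at week 10 (.36 / .72 / .36): .33 against .81–.83. The unconstrained joint test gives .64–.66.

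The adjusted average of the three post-baseline visits gives .84 for both the linear and the fading profile, but only .27 if the effect appears at week 15 alone.

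**6. Error if any visit could count.** Taking the largest of three correlated change contrasts, each at .025, gives about 6.5% per outcome by simulation. Over two independent co-primaries that is 1 − .935² = 12.6%.

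**The case against.** The best defence is that a saturated treatment-by-time model used for inference, with treatment and time as the independent variables, already means the interaction test. That is one test per outcome, the Bonferroni adjustment covers the outcomes, and Type I error is controlled. At alpha .025 this test keeps at least .80 power for two of the three profiles above, and for linear growth too if r is .6. The arithmetic also cannot prove which test the authors had in mind, because the joint test happens to give about .81–.83 for an effect that is full by week 10. Finally, the available text breaks off just before the general description of the mixed model, so wording there cannot be excluded. The H1a paragraph itself does survive, however, and it names no test.

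Most of this stands, and it rules out three stronger readings that a reader might infer.

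- **That either the power or the error control must fail.** It need not. The joint test controls error, and its power shortfall is conditional on effect shape, r and alpha.
- **That false positives reach about 12.6%.** This requires a rule that significance at any one visit suffices. The plan states no such rule; the phrase about effects emerging over the study is a hypothesis, not a decision rule.
- **That week 15 is the best single endpoint.** Its apparent advantage arises when only that contrast is adjusted for baseline. With equal adjustment the joint test is ahead in two of the three profiles. Week 15 is also five weeks after treatment ends, so fading is plausible. H2's use of week 15 follows mediators measured over weeks 0 to 10 and does not make it the H1a endpoint.

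The defence does not supply a stated test, or a power figure calculated for it.

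**Conclusion.** The point holds as a gap in specification with a conditional cost. The plan does not say which test of the saturated model decides H1a, and its .80 is expressed for a single contrast to which the model does not commit. Read as the 3-df interaction, power under linear growth is 8 to 10 points below the stated figure at alpha .025 and 13 to 16 points below at .0167. For an effect that is full by week 10 it is adequate at .025 and slightly short (.76–.78) at .0167. For an effect that is full by week 5 it is adequate at both.

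Separately, leaving baseline unconstrained costs power in every profile computed and under every test considered. This is the firmer part of the finding, because recovering that power needs no new data and no view about effect shape.

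The sizes rest on the assumed two-sided alphas, r = .5, compound symmetry and 39 complete cases per arm.

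**What to change.** 1. Keep the saturated mixed model, but constrain the arm means to be equal at week 0, which randomisation justifies, or move baseline from the outcome vector to a covariate.
2. Name one test per H1a outcome in advance: either the joint 3-df post-baseline test or one justified 1-df contrast (a stated visit or a post-baseline average). If the joint test is chosen, say how benefit will be established, since a significant joint test shows neither direction nor timing while H1a claims positive effects.
3. Label the remaining visit-level results as supportive.
4. State the numerical alpha per outcome, and restate power for the named test with an explicit effect profile over visits and a range for r.
5. Before naming any visit, reconcile the assessment times. The Procedure text gives 3, 12 and 15 weeks, whereas the Retention and H1a texts give 5, 10 and 15.

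The cost is wording in the analysis plan, with no added visits, participants or measurements. The choice in step 2 is a real trade-off: a week-15 contrast suits an effect that builds or persists, a post-baseline average suits one that fades, and the joint test covers more shapes at some loss against a well-chosen contrast. The investigators should justify that choice on what they expect after treatment stops, before seeing outcome data by arm.

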The subject population in this study will be 50 male and female O/O/O Veterans with mental health conditions and cognitive impairment served by the Aspire Center. It is anticipated that we will need to enroll and test 200 participants to end up with 98 who have cognitive impairment. We anticipate the top four mental health conditions to be PTSD, depression, history of substance use disorder, and history of TBI. Our inclusion criteria were selected in order to increase generalizability to other treatment-seeking homeless O/O/O Veterans with cognitive impairment. Participants will be men and women of any race/ethnicity, aged 18-55 years (which will represent the vast majority of O/O/O Veterans, but not introduce age-related dementing disorders as a confound). Complete inclusion/exclusion criteria are as follows:

Inclusion Criteria:

- 1) Male or female, any race/ethnicity, and age 18-55
- 2) Meets criteria for Aspire Center program entry
 - a) O/O/O Veteran
 - b) presence of at least one DSM-V mental health condition
 - c) does not meet criteria for substance use disorder for 28 days prior to admission
 - d) homeless or unstably housed (per HEARTH Act definition; HUD, 2011b)
 - e) not a sex offender or violent offender
 - f) capable of performing activities of daily living and transfers
 - g) not judged by a clinician to be at current risk to self or others
- 3) Has cognitive impairment in at least one cognitive domain (i.e., T-score < 40)
- 4) Able to speak and read English
- 5) Capable of and willing to provide signed informed consent

Exclusion Criteria:

None

Although it is recognized that the effects of chronic alcohol abuse can last longer than 28 days, the number of individuals in the study with recent alcohol abuse should be equally allocated across the two treatment groups by virtue of the power of randomization. In the unlikely event in a study this size that the treatment groups differ in this regard, alcohol history may be used as a covariate in the analyses.

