The sole recruitment source for this study will be the VA Aspire Center, a 40-bed Residential Rehabilitation Treatment Program serving homeless O/O/O Veterans with mental health conditions such as PTSD, depression, and TBI. A rate of accrual of 10 participants enrolled per quarter during the recruitment period (last three quarters of Year 1; Year 2; first quarter of Year 3) would be required to support our targeted accrual. The average length of stay is 3-6 months, meaning that between 80 and 160 participants per year would be eligible for the study. We aim to enroll 30 participants in the last three quarters of Year 1, 40 in Year 2, and 10 in the first quarter of Year 3, making our enrollment goals feasible. Our research team has held several planning meetings with the Aspire Center team and has identified a plan for successful recruitment that maximizes the possibility that participants will be enrolled while being minimally disruptive to Aspire Center operations. To facilitate recruitment, our PI and study staff will be highly visible at the Aspire Center and will coordinate with program intake staff (please see Letter of Support from [name], LCSW, Chief of the Aspire Center). Individuals who meet the inclusion criteria outlined above will then be approached for potential participation in the study and, if interested, will complete the consenting process and the baseline assessment.

Retention

During the trial, assessments will be administered at baseline, 5 weeks, 10 weeks, and 15 weeks, and brief monthly follow-up phone calls will assess housing and employment/education status for one year following program discharge. Participants will be compensated for their time spent in assessments (\$25 per assessment X 4 assessments = \$100 maximum total compensation) as a way to enhance retention. Based on prior studies of Veterans with PTSD and/or TBI, we expect about 20% attrition, for a final sample size of 78 (39 per group). Attrition may be even lower, given that all participants will be residing on-site. Monthly follow-up assessment of housing/employment status will be brief and not burdensome to participants.

Procedure

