Outcome assessment will occur at 3 weeks (treatment midpoint), 12 weeks (post-treatment), and 15 weeks (follow-up). Housing status and participation in work/school will be assessed by telephone monthly for 12 months following program discharge. Healthcare appointment attendance rates during the 12-month follow up period will be ascertained from CPRS records. We will maximize our data collection efforts by gathering participant cell phone numbers (most O/O/O Veterans, even those who are homeless, have cell phones). Furthermore, at baseline and discharge, we will obtain contact information for the Veteran and for at least two family members and close associates who can be contacted in case the Veteran cannot be contacted for monthly follow-up assessments of housing status. In the event that the Veteran still cannot be reached by telephone, we will use CPRS to track housing status (e.g., via V codes and progress notes), with appropriate HIPAA consent.

Table 1. Experimental and Control Conditions

Compensatory Cognitive Training (Appendix 1)	Education Control (Appendix 2)

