We have selected measures based on 4 criteria: 1) importance for assessing constructs in our theoretical model, 2) brevity (to reduce subject burden), 3) reliability, and 4) demonstrated validity.

Subject Characterization Measures

Measures of demographics, residential and vocational history, and history of alcohol and substance abuse will be administered by Aspire Center staff as part of the routine clinical intake process at program entry (Table 2). Subject characterization measures we will add (Table 3) include the Warrior Administered Retrospective Casualty Assessment Tool (WARCAT; Terrio et al., 2009), a short, structured interview of TBI history that allows for diagnosis of mild, moderate, or severe TBI based on the American Congress of Rehabilitation Medicine criteria, and the Wide Range Achievement Test-4 (Wilkinson et al., 2006) Reading subtest, which provides an estimate of premorbid IQ by measuring ability to read non-phonetically spelled English words.

Table 2. Measures Administered during Aspire Center Intake (no additional subject burden)

Measure	Construct Assessed
Demographic Form	Age, sex, education, race/ethnicity, marital status, service connection, medications prescribed
Residential Timeline Follow-Back (Tsemberis et al., 2007)	Residential history (number of days homeless, unstably housed, in an institution, or housed in the past 6 months)

Alcohol Use Disorders Identification Test (Saunders et al., 1993)	Alcohol use history
Drug Abuse Screening Test (Skinner, 1982)	Substance use history

Study Measures

Additional study measures are listed in Table 3 and further described below. Time required for these measures will be about 2 hours, 15 minutes, and breaks will be provided as needed by participants. We will administer a comprehensive, standardized battery at all four time points, including the following:

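### H1b measures housing stability only as months housed, with no rule for scoring a part-month loss, although the intake instrument already counts days in four housing states

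*Combined protocol and SAP*

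**What the plan says.** - **Outcome.** Section 9, Analytic Plan, H1b lists "Proportion of months housed, proportion of months engaged in productive activity (work or school") together with the proportion of VA appointments attended, "all three outcomes based on monthly data collected during the 1-year follow-up period". The months-housed variable is used again as a dependent variable in H2 and in exploratory Aim 3.
- **Collection.** Section 9, Procedure: "Housing status and participation in work/school will be assessed by telephone monthly for 12 months following program discharge". Family members or associates are contacted if the Veteran cannot be reached; failing that, "we will use CPRS to track housing status (e.g., via V codes and progress notes").
- **Burden.** Section 9, Retention: "Monthly follow-up assessment of housing/employment status will be brief and not burdensome to participants".
- **Missing months.** H1b: "Any missing data on housing and work/school status will be accounted for by using a proportion based on the available data points".
- **Intake.** Table 2 lists the Residential Timeline Follow-Back, given by program staff at entry: "Residential history (number of days homeless, unstably housed, in an institution, or housed in the past 6 months"). It is not listed for follow-up.
- **Eligibility.** Criterion 2d admits a Veteran who is "homeless or unstably housed (per HEARTH Act definition; HUD, 2011b").
- **Covariates.** The H1b ANOVA may include covariates that turn out imbalanced between groups. None is prespecified for housing.

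The documents give no call script, recall window or status categories, and no rule for when a month counts as housed.

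**The concern.** Housing stability is partly about short losses of housing, and a month-level measure has a step of 1/12 of the year. The missing scoring rule matters as much as the step. Someone must decide whether a month with ten nights in a shelter, a month on an acquaintance's sofa, or a month in a hospital or jail counts as housed. Unstable housing is one of the two conditions that qualify a Veteran for the trial, yet the follow-up measure has no stated place for it. Intake meanwhile separates exactly these states, in days.

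At stake are precision in a comparison sized only for a medium-to-large effect, and the meaning of the housing result wherever it is used (H1b, H2, Aim 3).

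**Working it through.** **1. The plan's own figure.** H1b states .80 power for an effect of .64 with 39 per group. No numeric alpha is given. At an assumed unadjusted two-sided .05, the noncentral t gives .797 and the normal approximation .807, so the figure reproduces. It is not disputed here.

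**2. Resolution for a single loss, if the call records status that day.** The chance that a spell of L days covers a call date is L/30.4. Each call date covered costs 1/12 = 8.3% of the year.

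| Spell (days) | Chance seen | True share of year |
|---|---|---|
| 7 | 7/30.4 = .23 | 1.9% |
| 14 | 14/30.4 = .46 | 3.8% |
| 30 | 30/30.4 = .99 | 8.2% |

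The expected score is right: for 14 days, .46 × 8.3% = 3.8%. The individual's score is coarse, but the average is not biased.

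**3. Precision under call-day status.** The model is a two-state daily housing process over 365 days, started in its stationary state, with 20,000 simulated Veterans per scenario and every call completed. The ratio is the variance of the 12-call proportion divided by the variance of the daily proportion. All spell lengths are assumed. Two independent runs gave:

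| Mean days housed / unhoused | Variance ratio | Share of Veterans with a loss who score 12 of 12 |
|---|---|---|
| 90 / 14 | 1.52, 1.57 | .18, .19 |
| 180 / 14 | 1.48, 1.47 | .35, .36 |
| 90 / 30 | 1.18, 1.19 | .07, .07 |
| 180 / 30 | 1.14, 1.13 | .17, .18 |
| 365 / 30 | 1.12, 1.13 | .28, .28 |
| 180 / 60 | 1.06, 1.06 | .09, .09 |
| 365 / 90 | 1.03, 1.03 | .11, .11 |

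Group means from calls and from days agreed within .001 in every scenario (for example .864 and .864; .925 and .925). This model gives every Veteran the same risk. With assumed lognormal variation in risk (SD 1.0-1.5), the ratios fall to about 1.12-1.22 for 14-day spells and 1.02-1.10 for longer ones.

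**4. What the ratio means for the comparison.** Because call-day means are unbiased, the raw group difference is the same on both measures and only the SD changes. If .64 belongs to the planned monthly measure, day counts would give .64 × √ratio: .64 × √1.03 = .65, .64 × √1.20 = .70, and at the extreme .64 × √1.57 = .80.

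**5. Whole-month scoring.** A second simulation assumed a mean of one spell per person-year with risk varying between people. The mean proportion housed was:

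| Mean spell (days) | Days | Call-day | Majority of month | Any loss makes the month unhoused |
|---|---|---|---|---|
| 7 | .981 | .981 | .993 | .910 |
| 14 | .964 | .963 | .974 | .897 |
| 30 | .930 | .927 | .937 | .869 |

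For 14-day spells the true loss of 1 − .964 = 3.6% is recorded as 2.6% under the majority rule and as 10.3% under the any-loss rule. The scoring rule therefore changes what is measured, and the plan does not choose one.

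**6. The covariate.** Adjusting for a baseline covariate with correlation ρ raises the standardised effect to .64/√(1 − ρ²). For an assumed ρ of .2 this is .64/.980 = .653, power about .81. For ρ of .4 it is .64/.917 = .698, power about .86. Unadjusted power is .80.

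**The case against.** The strongest reply is that this is a preference for a finer measure on an outcome that is not co-primary. The plan keeps calls short on purpose, and compensation covers the four assessments, not the calls. The fallback sources can support a monthly status but perhaps not day counts. Recall by day is asked of people selected for cognitive impairment. The intake instrument is routine program intake, used to characterise subjects. A proportion of days is itself a quantity of housing: it counts no moves, and a 7-day loss scores 98%. All of this stands, and it limits the fix, but it does not supply the missing scoring rule.

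Three stronger readings are tempting, and the documents do not support them:

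- *The outcome is one binary status per call.* A reader might infer this, but only a status and a monthly proportion are named. The rule is unstated.
- *Veterans who lose housing are scored as perfectly housed, so the result is biased.* Under call-day status some do score 12 of 12, but they were housed a median 95-98% of days and the group means are unbiased. Under an any-loss rule, fewer than 1% of Veterans with a loss score 12 of 12.
- *The stated .80 power is overstated because of this noise.* The .64 is a standardised effect for the planned outcome, so its SD already contains the noise. Power falls only if .64 is assigned to a day-count measure that the plan does not use.

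Nor is a mismatch of scale between intake and outcome a defect in itself. A covariate need not share the outcome's scale.

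**Conclusion.** The point holds as a low-severity improvement. As written, the H1b housing outcome cannot resolve losses shorter than a month, and the scoring of part-month loss, unstable housing and institutional stays is undefined.

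Under call-day scoring the consequence is lost precision without bias in the group means: about 3-20% more variance than day counts for spells of 30 days or more, and about 20-57% more for 14-day spells. The lower parts of these ranges, or slightly below them (2% and 12%), apply when risk varies widely between Veterans. Under whole-month scoring, short losses are rounded down or up. No revised power or sample size follows, because the documents give neither spell lengths nor a day-level SD. If spells typically last two to three months, the precision gain is negligible and the main benefit is a defined outcome.

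The covariate is a separate gain. Its size depends on a correlation that the documents do not give.

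**What to change.** 1. At each monthly call, record the number of days since the last call spent in each of the four intake states: homeless, unstably housed, in an institution, housed.
2. Make the proportion of days housed the H1b housing variable, and carry it into H2 and Aim 3.
3. Keep the months-housed proportion as a supporting summary, with a written rule for when a month counts as housed. It also covers months known only from contacts or CPRS.
4. Report institution days separately, with a sensitivity analysis for how they are classed. Counting them as not housed is debatable, and the documents do not settle it.
5. Separately, prespecify the intake 6-month proportion of days housed as a covariate in the H1b housing model, whether or not the groups look imbalanced. The data are already collected at intake, so this needs only a line in the analysis plan.

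The cost of items 1-4 is a slightly longer call, about 30 days of recall in a cognitively impaired sample (intake already asks for 6 months), and day counts that may be missing when only CPRS data are available. If the calls cannot be lengthened, the written rule in item 3 is the minimum.
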